Subjects will undergo bone marrow examination no later than Day 42 of Induction Cycle 1 for assessment of response. Subjects with \geq 5% residual leukemic blasts in bone marrow will receive Induction Cycle 2 as outlined in [Synopsis Table 1](#), which may be administered prior to blood count recovery. Subjects with <5% residual blasts will receive Consolidation Cycle 1 as outlined in [Synopsis Table 2](#) upon recovery of peripheral blood counts (absolute neutrophil count [ANC] > 1.0×10^9 /L; platelet count > 100×10^9 /L). After completion of Induction Cycle 2 or Consolidation Cycle 1 (hereafter referred to collectively as Chemotherapy Cycle 2), subjects will undergo bone marrow examination for assessment of remission status at the investigative site (bone marrow biopsy is mandated if sufficient or adequate aspirate cannot be obtained, eg, due to dry tap, hemodilution or hypocellularity). Bone marrow examination should await recovery of ANC to > 1.0×10^9 /L and platelet count to > 100×10^9 /L later than Day 42 of Chemotherapy Cycle 2, unless leukemic progression is suspected. Subjects who achieve or remain in morphologic CR after Chemotherapy Cycle 2 will undergo MRD assessment in peripheral blood and bone marrow aspirate in a central laboratory designated by the Sponsor. Subjects who have not achieved morphologic CR after the last cycle of induction (whether it be Induction Cycle 1 or Induction Cycle 2) will be deemed treatment failures. [Figure 4](#) provides a schematic representation of the study treatment plan from Cycle 1, Day 1 through completion of Chemotherapy Cycle 2.

Subjects who achieve MRD negative CR status post-induction will undergo retrospective MRD assessments in peripheral blood every 3 months until morphologic relapse.

All subjects who achieve morphologic CR, CRh, or CRi upon completion of Chemotherapy Cycle 2 may initiate or continue consolidation therapy in combination with ENTO or placebo (in

CONFIDENTIAL

Protocol KB-ENTO-3001 v4.0 Global
(Amendment 3.0 Global)

accordance with their original randomized treatment assignment), as outlined in [Synopsis Table 2](#) at the investigator's discretion either instead of or as a bridge to hematopoietic stem cell transplant.

Synopsis Table 2: Treatment Phase –Consolidation

	Age < 60 years	Age ≥ 60 years
Cytarabine	3.0 g/m ² , BID over 3 hours on Days 1, 3 and 5 every 28-35 days for up to 3 cycles*	1.5 g/m ² , BID over 3 hours on Days 1, 3 and 5 every 28-35 days for up to 3 cycles*

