Cytarabine	1.0 g/m ² , BID Days 1-6	1.0 g/m ² , BID Days 1-6
Anthracycline	Daunorubicin, 60 mg/m ² slow IV push, Days 1-3 OR Idarubicin, 12 mg/m ² slow IV push, Days 1-3	N/A

Abbreviations: BID, twice daily; IV, intravenous; N/A, not administered.

^a Subjects who are candidates for continuous infusion of cytarabine in Cycle 1 at doses higher than 100 mg/m²/day are ineligible.

Subjects will undergo bone marrow examination no later than Day 42 of Induction Cycle 1 for assessment of response. Subjects with $\geq 5\%$ residual leukemic blasts in bone marrow will receive Induction Cycle 2 as outlined in [Table 4](#), which may be administered prior to blood count recovery. Subjects with $< 5\%$ residual blasts will receive Consolidation Cycle 1 as outlined in [Table 5](#) upon recovery of peripheral blood counts (absolute neutrophil count [ANC] $> 1.0 \times 10^9/L$; platelet count $> 100 \times 10^9/L$). After completion of Induction Cycle 2 or Consolidation Cycle 1 (hereafter referred to collectively as Chemotherapy Cycle 2), subjects will undergo bone marrow examination for assessment of remission status at the investigative site (bone marrow biopsy is mandated if sufficient or adequate aspirate cannot be obtained, eg, due to dry tap, hemodilution or hypocellularity). Bone marrow examination should await recovery of ANC to $> 1.0 \times 10^9/L$ and platelet count to $> 100 \times 10^9/L$ no later than Day 42 of Chemotherapy Cycle 2, unless leukemic progression is suspected. Subjects who achieve or remain in morphologic CR after Chemotherapy Cycle 2 will undergo MRD assessment in peripheral blood and bone marrow aspirate in a central laboratory designated by the Sponsor. Subjects who have not achieved morphologic CR after the last cycle of induction (whether it be Induction Cycle 1 or Induction Cycle 2) will be deemed treatment failures. [Figure 4](#) provides a schematic representation of the study treatment plan from Cycle 1, Day 1 through completion of Chemotherapy Cycle 2.

Figure 4 Treatment Phase: Cycle 1, Day 1 through Completion of Chemotherapy Cycle 2:

* Following recovery of ANC to $>1.0 \times 10^9 / \text{L}$ and platelet count to $>100 \times 10^9 / \text{L}$
 BMA, bone marrow aspirate; MRD, measurable residual disease

Subjects who achieve MRD negative CR post-Chemotherapy Cycle 2 will undergo retrospective MRD assessments in peripheral blood every 3 months until morphologic relapse.

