NPM1-m MRD assessments ^r	X						X			X	X
Pharmacokinetics ^s		X	X	X				X		X	
Peripheral blood biomarker assessments ^t	X	X	X	X			X	X		X	X
Bone marrow aspirate biomarker assessments ^u	X						X				
Pharmacogenomics (whole blood) ^v	X										
Patient reported outcomes ^w	X						X			X	X
Follow-up for relapse, first salvage therapy, OS ^x											X

CONFIDENTIAL

Protocol KB-ENTO-3001 v4.0
(Amendment 3.0)

Abbreviations: AEs, adverse events; AML, acute myeloid leukemia; β -HCG, beta human chorionic gonadotropin; ECG, electrocardiogram; ECHO, echocardiogram; ECOG PS, Eastern Cooperative Oncology Group Performance Status; FSH, follicle stimulating hormone; HBV, hepatitis B virus; HCV, hepatitis C virus; HIV, human immunodeficiency virus; LFTs, liver function studies; MUGA, multi-gated acquisition; *NPM1*-m, *Nucleophosmin 1*-mutated; MRD, measurable residual disease; OS, overall survival.

* Subjects with $\geq 5\%$ residual leukemic blasts in bone marrow aspirate between Days 14 and 28 of Induction Cycle 1 will receive Induction Cycle 2 as outlined in [Table 4](#), which may be administered prior to blood count recovery. Subjects who have achieved a complete response (CR) either with or without full hematologic recovery (CRh, CRi) or a morphologic-free leukemia state (MFLS) will proceed to Consolidation Cycle 1 ([Table 5](#)) upon recovery of peripheral blood counts (absolute neutrophil count [ANC] $\geq 1.0 \times 10^9/L$; platelet count $\geq 50 \times 10^9/L$). After completion of Induction Cycle 2 or Consolidation Cycle 1 (ie. Chemotherapy Cycle 2), subjects will undergo bone marrow examination for assessment of remission status at the investigative site. Patients in morphologic CR post-Chemotherapy Cycle 2 will undergo MRD assessment (see footnote "r" below).

^a Acceptable windows for study visits/assessments after C1D1 are ± 1 day; however, study treatment must be administered on the days indicated (eg, Days 1-7 for cytarabine, and Days 1-3 for daunorubicin or idarubicin in Induction Cycle 1).

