ⁱ Includes hemoglobin, hematocrit, WBC and platelet counts, and WBC differential (neutrophils, bands, lymphocytes, monocytes, eosinophils, basophils, blasts). At times not designated in Table 7, monitor CBC and WBC differential in accordance with institutional care standards until ANC is $>1.0 \times 10^9/L$ or persistent leukemia is documented. Monitor platelet counts at times designated in Table 7 and at other times, per institutional care standards until the platelet count is $>100 \times 10^9/L$ or persistent leukemia is documented. Monitor CBC and platelet count twice weekly during consolidation and at other times, as clinically indicated.

^j Includes electrolytes (sodium, potassium, chloride, total CO₂ and/or bicarbonate, calcium, phosphate), liver function studies (aspartate aminotransferase [AST], alanine aminotransferase [ALT], total and direct bilirubin), lactate dehydrogenase (LDH), alkaline phosphatase, blood urea nitrogen [BUN] or serum urea, creatinine, uric acid, glucose, amylase, and lipase. Include total creatine phosphokinase (CPK) at Screening, Day 14 of each induction cycle, and End of Study Treatment. At times not designated in Table 7, monitor electrolytes, LFTs, BUN, creatinine, uric acid, and phosphate in accordance with institutional care standards until the risk of tumor lysis syndrome has abated. For subjects

CONFIDENTIAL

Protocol KB-ENTO-3001 v4.0
(Amendment 3.0)

receiving nephrotoxic antimicrobial agents, closer monitoring of renal function throughout the period of hospitalization is recommended, consistent with institutional standards of care.

^k Includes prothrombin time, activated partial thromboplastin time and international normalized ratio. Perform coagulation panel twice per week during Induction. For subjects with evidence of disseminated intravascular coagulation (DIC), coagulation parameters including fibrinogen should be monitored in accordance with institutional care standards until resolution.

^l Includes dipstick evaluation for pH, glucose, protein, blood, leukocyte esterase and microscopic evaluation for red and white blood cells. After Screening, perform urinalysis as clinically indicated.

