9.4.3 Secondary Endpoint(s)

The secondary endpoint variables and their population level summary measures will be described in each of the following sections. The evaluation of the population for the trial, treatments of interest, and the possible intercurrent events are as described in [Section 9.4.2.1](#). All secondary endpoints will include death as part of definition of the variable. Intercurrent events of additional leukemic therapy and premature study treatment discontinuation will be ignored for the primary evaluation of these endpoints. Additional information on the handling of missing data and sensitivity analyses will be detailed in the SAP.

CONFIDENTIAL

Protocol KB-ENTO-3001 v4.0

(Amendment 3.0)

Event-free survival

Event-free survival (EFS) is defined as time from randomization to the earliest of induction treatment failure (ITF), relapse for those who achieve CR, or death from any cause. ITF is failure to achieve morphological CR after completion of the last cycle of induction chemotherapy (no later than Day 42 of the last cycle of induction). Subjects who experience ITF will be treated as events at Day 1.

Subjects who do not experience an event (ITF, relapse from CR, or death) will be censored at their last study evaluation at which they were relapse free. Event-free survival will be estimated using the method of Kaplan-Meier (K-M) and summarized by treatment group. Differences between the treatment groups will be assessed with the log rank test stratified by age (<60 vs \geq 60 years) and choice of anthracycline in induction (daunorubicin vs idarubicin). The population level summary measure will be the adjusted hazard ratio as calculated from a Cox proportional hazards model with effects for treatment, age, and choice of anthracycline in induction.

Relapse free survival

For subjects who achieve CR, relapse free survival (RFS) is defined as the time from CR to morphologic relapse as assessed by the study site investigator or death from any cause, whichever comes first. Subjects who do not experience a relapse or death will be censored at the last study evaluation at which they were relapse free. RFS will be estimated using the K-M method and summarized by treatment group. The population level summary measure will be the adjusted hazard ratio as calculated from a Cox proportional hazards model with effects for treatment, age, and choice of anthracycline in induction.

Overall survival

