2.1. Study Overview

This is a Phase 3, multi-center, international, double-blind, placebo-controlled study in previously untreated subjects with Acute Myeloid Leukemia (AML) harboring *nucleophosmin-1 (NPM1)* mutations. Subjects will be randomized 1:1 to receive intensive induction chemotherapy in combination with either the spleen tyrosine kinase (SYK) inhibitor, entospletinib (ENTO), or placebo. Randomization will be stratified by age (<60 or \geq 60 years) and anthracycline administered during induction (daunorubicin vs idarubicin). The study will consist of Screening, Induction, Consolidation, End-of-Treatment, and Long-term Follow-up phases.

ENTO (400 mg) or placebo will be administered continuously twice daily (BID) approximately every 12 hours beginning on Cycle 1 Day 1 of induction chemotherapy (**Table 1**) through completion of consolidation (**Table 2**), including while awaiting blood count recovery.

Subjects will undergo bone marrow examination no later than Day 42 of Induction Cycle 1 for assessment of response. Subjects with \geq 5% residual leukemic blasts in bone marrow will receive Induction Cycle 2 as outlined in **Table 1**, which may be administered prior to blood count recovery. Subjects with <5% residual blasts will receive Consolidation Cycle 1 as outlined in **Table 2** upon recovery of peripheral blood counts (absolute neutrophil count [ANC] $>$ 1.0 \times 10⁹/L; platelet count $>$ 100 \times 10⁹/L).

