Patient reported outcomes ^w	X						X					X	X
Follow-up for relapse, first salvage therapy, OS ^x													X

Abbreviations: AEs, adverse events; AML, acute myeloid leukemia; β -HCG, beta human chorionic gonadotropin; ECG, electrocardiogram; ECHO, echocardiogram; ECOG PS, Eastern Cooperative Oncology Group Performance Status; FSH, follicle stimulating hormone; HBV, hepatitis B virus; HCV, hepatitis C virus; HIV, human immunodeficiency virus; LFTs, liver function studies; MUGA, multi-gated acquisition; *NPM1*-m, *Nucleophosmin 1*-mutated; MRD, measurable residual disease; OS, overall survival.

* Subjects with $\geq 5\%$ residual leukemic blasts in bone marrow aspirate performed no later than Day 42 of Induction Cycle 1 will receive Induction Cycle 2 as outlined in Table 1, which may be administered prior to blood count recovery. Subjects with $<5\%$ leukemic blasts will proceed to Consolidation Cycle 1 (Table 2) upon recovery of peripheral blood counts ($ANC \geq 1.0 \times 10^9/L$; platelet count $\geq 50 \times 10^9/L$). After completion of Induction Cycle 2 or Consolidation Cycle 1 (i.e., Chemotherapy Cycle 2), subjects will undergo bone marrow examination for assessment of remission status at the investigative site. Patients in morphologic CR post-Chemotherapy Cycle 2 will undergo MRD assessment (see footnote “r” below).

^aAcceptable windows for study visits/assessments after Cycle 1 Day 1 (C1D1) are ± 1 day; however, study treatment must be administered on the days indicated (e.g., Days 1-7 for cytarabine, and Days 1-3 for daunorubicin or idarubicin in Induction Cycle 1).

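### Table 7 footnote * starts Consolidation Cycle 1 at platelets of 50 or more, the Synopsis and Section 4.1 require more than 100, and nothing says which rule prevails

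*Protocol*

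**What the plan says.** After Induction Cycle 1, a subject whose marrow has cleared to under 5% blasts goes to Consolidation Cycle 1 once blood counts recover. Recovery is defined in two ways.

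- Protocol Section 4.1: "upon recovery of peripheral blood counts (absolute neutrophil count [ANC] $> 1.0 \times 10^9/L$; platelet count $> 100 \times 10^9/L". The Synopsis gives the same values: "upon recovery of peripheral blood counts (absolute neutrophil count [ANC] > 1.0×10^9 /L; platelet count > 100×10^9 /L".
- Protocol Table 7, footnote *: "upon recovery of peripheral blood counts (absolute neutrophil count [ANC] $\geq 1.0 \times 10^9/L$; platelet count $\geq 50 \times 10^9/L".
- SAP Section 2.1 follows the main text: "upon recovery of peripheral blood counts (absolute neutrophil count [ANC] $>$ 1.0 \times 10⁹/L; platelet count $>$ 100 \times 10⁹/L".
- SAP Section 2.2, footnote *, follows the table: "upon recovery of peripheral blood counts ($ANC \geq 1.0 \times 10^9/L$; platelet count $\geq 50 \times 10^9/L".

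Footnote i of Table 7 has platelets monitored "until the platelet count is $>100 \times 10^9/L$ or persistent leukemia is documented".

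Two further rules bear on the consequence. The failure rule is in Section 4.1: "not achieved morphologic CR after the last cycle of induction (whether it be Induction Cycle 1 or Induction Cycle 2) will be deemed treatment failures". Section 9.4.3 sets the deadline and the event date: "no later than Day 42 of the last cycle of induction). Subjects who experience ITF will be treated as events at Day 1".

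**The concern.** The count threshold decides when the next course of chemotherapy begins, at 3.0 or 1.5 g/m² of cytarabine twice daily depending on age. A site working from the schedule table would dose a subject with platelets of 60. A site working from Section 4.1 would hold the same subject.

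The conflict also affects deviation review. SAP Section 7 has the project team review deviations before unblinding to pick out the important ones. With two thresholds in force, nobody can say whether a start at 50 to 100 was a deviation.

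A secondary question is whether the timing of that start can change a subject's EFS status.

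**Working it through.** No formula or planned figure is involved, so the check is a comparison of the texts.

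**Step 1. The rule in each place (ANC and platelets × 10⁹/L).**

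| Place | Who proceeds | ANC | Platelets |
|---|---|---|---|
| Protocol Synopsis | <5% blasts | >1.0 | >100 |
| Protocol 4.1 | <5% blasts | >1.0 | >100 |
| Protocol Table 7, footnote * | CR, CRh, CRi or morphologic leukemia-free state | ≥1.0 | ≥50 |
| SAP 2.1 | <5% blasts | >1.0 | >100 |
| SAP 2.2, footnote * | <5% blasts | ≥1.0 | ≥50 |

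The notes under protocol Figure 4 and SAP Figure 1 also use >1.0 and >100. The drawings themselves could not be seen, so these count only as support. No text limits the lower threshold to a subgroup or exception.

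**Step 2. Where the rules disagree (under 5% blasts, ANC above 1.0).**

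- Platelets below 50: every version says wait.
- Platelets 50 to 100 inclusive: both footnotes say start; the Synopsis, Section 4.1 and SAP 2.1 say wait.
- Platelets above 100: every version says start.

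The different ANC signs matter only at exactly 1.0.

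**Step 3. Response status in the disputed range.** Appendix 4 requires platelets above 100 for CR. With the other CR criteria met, a subject above 50 and up to 100 is CRh, and at exactly 50 is CRi. Neither is CR.

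**Step 4. The route to EFS.** For a subject with under 5% blasts, Induction Cycle 1 is the last induction cycle. A changed EFS status needs three things together:

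1. the site starts consolidation at 50 to 100;
2. the subject would otherwise have passed 100 by Day 42;
3. no CR is documented by Day 42.

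That subject becomes an induction treatment failure with an event at Day 1, yet could still be an MRD-negative CR on the primary endpoint after Chemotherapy Cycle 2. A subject who would still be at 50 to 100 on Day 42 fails under either rule, so the conflict changes nothing there.

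**Step 5. Why no size is attached to Step 4.** The documents give no frequency for any of the three conditions. The CR rates in Section 9.2 do not supply a yardstick for two reasons.

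- The 87% is labelled CR there, but Section 2.2 reports 13 of 15 (13/15 = 87%) as CR or CRi, and CRi can include subjects with platelets at or below 100. So 1 − 0.87 is not a CR failure rate.
- The Section 9.2 rates feed the endpoint after Chemotherapy Cycle 2, whereas induction failure is judged at the last induction cycle.

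**Step 6. A smaller mismatch in the same footnote.** The protocol footnote times the Cycle 1 marrow at Days 14 to 28. Section 4.1, footnote q and the SAP footnote all set a limit of Day 42. A marrow on Days 14 to 28 meets that limit, but the footnote leaves Days 29 to 42 uncovered.

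**The case against.** **The lower threshold may be deliberate.** A threshold for starting chemotherapy need not equal a threshold for response. Footnote * names CRh, CRi and the leukemia-free state, and its 50 is close to the CRh platelet cut-off. Section 4.1 lets CRh and CRi subjects have consolidation after Chemotherapy Cycle 2, and Section 7.1 stops study medication only when none of CR, CRh or CRi is reached. This stands as far as it goes: consistency with the CR definition is not a decisive reason to choose 100. The better reason is that the Synopsis and Section 4.1 both state it. Even if 50 was intended, sites would still need one value.

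**The EFS consequence is hypothetical.** This stands too. It needs three conditions together. The same discordance, an EFS event at Day 1 alongside a primary-endpoint success, also arises under the higher threshold whenever platelets recover only after Day 42. It comes from the induction failure rule, and the footnote can only add cases.

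**Footnote i is a monitoring instruction.** Agreed. It does not set a treatment threshold, so it does not settle the matter.

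**The SAP copy reaches no patient.** Agreed. The SAP Introduction sends readers to the protocol for study conduct.

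**The trial is over.** SAP Section 4.2 records 15 randomized subjects, and Section 6.4 drops all protocol-defined primary and secondary efficacy analyses. That removes any effect on reported efficacy results. It does not remove the conflict in the instructions while sites were treating, or the difficulty in classifying deviations.

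**Conclusion.** The inconsistency is certain. Each document contradicts itself on an operative treatment rule, across the whole platelet range from 50 to 100, with no precedence stated. The main consequences are that identical patients could be treated differently and that a start in that range cannot be classified as compliant or not.

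The EFS consequence is possible, secondary and unquantified. A reader might infer that the footnote would have added a material number of Day-1 events, biased EFS or reduced its power. The documents do not support that: they give no frequency, no reason for the arms to differ, and no reliable count of induction failures to compare against.

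The conclusion rests on the text alone and needs no numerical assumption. It concerns the design and the instructions to sites, not reported results.

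**What to change.** Make these changes to protocol Table 7, footnote *, by amendment:

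1. Replace the list of response categories with *subjects with <5% leukemic blasts*, as the SAP footnote already has it. If only the threshold were changed, the footnote would still name categories defined by incomplete recovery while requiring full recovery.
2. Set the threshold to ANC >1.0 × 10⁹/L and platelets >100 × 10⁹/L, matching Section 4.1.
3. Change the marrow timing from Days 14 to 28 to no later than Day 42.
4. In the same amendment, state what happens to a subject with under 5% blasts whose platelets have not passed 100 by Day 42. Footnote * is at present the only text that lets such a subject proceed, and Section 4.1 names no path. This is a treatment rule, so a site memo is not enough.

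Correct the threshold in SAP Section 2.2, footnote *, for consistency; this changes nothing at sites.

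The cost is amendment approval: Appendix 1 (Section 10.1.1) requires IRB/IEC approval, and health authority approval for substantial changes where applicable. The other cost is losing the earlier start that the footnote allowed at 50 to 100. No procedure is added.

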8.1 Informed Consent

Study site personnel must obtain signed informed consent before any study-specific procedures (including central laboratory screening for the presence of *NPM1* and *FLT3* mutations) are conducted unless these are part of the standard of care and must document the informed consent process in the patient's medical record. Consent must be obtained using the most current version of ICF approved by the study site's Institutional Review Board (IRB)/Independent Ethics Committee (IEC). Once the patient signs the ICF, that will signal the beginning of the 14-day Screening Period. Selected screening assessments may be repeated once for final eligibility determination if thought to be out-of-range due to artifact or transient abnormality. These include the following: ECG, ECHO, clinical chemistries/liver function studies, coagulation screening studies and HBV/HCV/HIV serologies.

